## Eligibility Criteria

### **Youth Inclusion Criteria:**

- Youth aged 12-26 yo
- Own a cell phone with text message capability
- Biological or adoptive parent is willing to provide informed consent for teen to participate
- Youth speaks and understands English

-Positive PHQ score or provider determines youth has depressive symptoms based on clinical interaction and refers youth to the study (in cases when PHQ is not available and study staff will complete the PHQ during the screening) OR Provider can refer if they are unclear if symptoms are depressive and PHQ scoring will be used to determine youth's eligibility. OR Screening Wizard screening questionnaire (which includes the PHQ and depressive symptom questions) indicates depression OR provider indicates there is a concern that youth has mood or behavioral problem.

-Referred to mental health care OR screening wizard questionnaire (which indicates if provider makes referral to mental health care)

PHQ-9 scores:

Score of 8 or higher on PHQ-8 -or-

Score of 1 or higher on #9 of PHQ-9 suicidality item

#### **Parent inclusion criteria:**

- Age 18 or older
- Own a cell phone with text message capability
- Speaks and understands English
- Parent of a youth that scores positive on the PHQ-8 or #9 as described above
- Parent of a youth who has been referred to mental health treatment

#### **Youth Exclusion Criteria:**

- Non English speaking
- No parent willing to provide informed consent
- No cell phone with text messaging capability
- Is currently experiencing mania or psychosis
- Evidence of an intellectual or developmental disorder (IDD)
- Life threatening medical condition that requires immediate treatment
- Other cognitive or medical condition preventing youth from understanding study and/or participating.
- Not referred to mental health care

#### **Parent Exclusion Criteria:**

- No cell phone with text messaging capability
- Child meets exclusion criteria as described above
- Other cognitive or medical condition preventing parent from understanding study and/or participating.

## **Statistical Considerations**

A stepped wedge design was selected for both ethical considerations and feasibility. A stepped wedge cluster randomized trial design involves the sequential random rollout of an intervention over multiple time periods following a “baseline” period when no cluster has been exposed. The

crossover is typically in one direction, from control to intervention, and continues until all of the clusters receive the intervention with observations taken from every cluster and at each time period. All 3 studies in the ETUDES Center, and specifically, T2C, will utilize this design. Prior to study start, each CCP study practice will be randomly assigned to switch from Treatment As Usual (TAU) to the intervention.

In the proposed stepped wedge design, all practices start with TAU (i.e., PCP referral to embedded MH care) and are randomized to transition to implement T2C at different times. All clinics will be initially monitored for at least 2 months during TAU, followed by a staggered adoption of T2C. During each time period, a new clinic will begin to use T2C (order determined by block randomization. A web-based system will randomly assign the next clinic to begin.

With regard to Hypothesis 1: We will conduct t tests for continuous variables and chi square tests for categorical variables to examine for baseline differences in demographic and clinical variables. We will use generalized linear mixed models (nesting for site) to examine for between-intervention differences in readiness. Baseline characteristics that distinguish the groups will be included as covariates in models examining treatment effects.

In order to enhance uptake of T2C, we will conduct the proposed work within the RE-AIM framework, as follows. (R)each: The percentage and characteristics of screen-positive adolescents referred for MH treatment who are offered, and agree to participate in, T2C. (E)fficacy: The impact of T2C on MH treatment initiation and engagement. (A)doption: The percentage and characteristics of PCPs who refer to T2C upon making a referral for MH care for a screen-positive adolescent. (I)mplementation: The percentage and characteristics of patients who consent to T2C who complete the TM intervention. (M)aintenance: The percentage and characteristics of PCPs who recommend T2C to appropriate patients upon long-term follow-up, as well as T2C utilization by referred adolescents/parents via de-identified data. The baseline and follow up measures administered are mapped onto each component of the RE-AIM framework.

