## Study Objectives

To increase rates of MH care initiation, we propose an automated TM intervention, “Text to Connect” (T2C), that aims to increase motivations in at-risk adolescents and their parents. We will develop and examine T2C using dissemination and implementation science principles, specifically, the RE-AIM framework, for balancing internal and external validity and optimizing uptake and sustainability. We will select the most salient of the following behavior change techniques: psychoeducation, cued mood monitoring, adolescent-parent communication prompts, cognitive bias modification, and cues to action. Intervention material will be tailored to baseline characteristics. We will begin with treatment development. In an initial usability phase, we will develop and iteratively refine the format and content of T2C based on feedback from stakeholders. Data will inform a subsequent feasibility trial comparing T2C with treatment as usual (TAU) using a stepped wedge design.

Aim 1 (Phase 1, Development). To develop T2C, a TM intervention to address motivational barriers to MH treatment initiation for depression and/or suicidal screen-positive adolescents and parents in pediatric primary care. We will collaborate with NuRelm and the Office of Academic Computing at WPIC and the Methods Core to develop T2C based on stakeholder feedback (adolescents, parents, pediatricians, MH clinicians).

Aim 1b (Phase 1b, Feasibility). To examine the feasibility of T2C in pediatric primary care clinics (n=2 clinics, 50 adolescents) using a stepped wedge design.

Hypothesis 1b: Readiness for MH care will be greater among adolescents in T2C vs adolescents referred during TAU. We will first conduct t tests for continuous variables and chi square tests for categorical variables to examine for baseline differences in demographic

and clinical variables. We will use generalized linear mixed models (nesting for site) to examine for between-intervention differences in readiness. Baseline characteristics that distinguish the groups will be included as covariates in models examining treatment effects.

Aim 2: Explore differential rates of service utilization (behavioral and physical health services) among youth who receive Text2Connect (T2C) versus Treatment As Usual (TAU).

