A stepped wedge design was selected for both ethical considerations and feasibility. First, the T2C intervention is unlikely to cause harm, and PCP stakeholders have expressed the need and desire for these tools. Thus, we will offer these interventions to all practices to maximize stakeholder feedback and optimize opportunities for implementation. In the proposed stepped wedge design, all practices start with Treatment As Usual-TAU-(i.e., PCP referral to Mental Health care) and are randomized to transition to implement T2C at different times. All clinics will be initially monitored for at least 2 months during TAU, followed by a staggered adoption of T2C. During each time period, a new clinic will begin to use T2C (order determined by block randomization. A web-based system will randomly assign the next clinic to begin.

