#### Baseline assessment phone call:

Following the informed consent, the ARC assessor will conduct the baseline assessment measures. The measures include collecting sociodemographic questions, the CSSRS scale & suicide scales, quality of life ratings, treatment history, barriers to treatment, readiness for treatment, attitudes toward seeking psychological help, anxiety & mania adaptive scales via the K-CAT mental health adaptive screen, substance use, depression history, treatment preferences, and if there's a family history of bipolar disorder that impacts the youth's risk for mental health problems. A waiver of HIPAA authorization to collect permission verbally over the phone will be used to access and collect medical record data. Electronic medical record information will be used to supplement treatment and service utilization and uptake of the T2C intervention via the RE-AIM framework described in statistical analysis. Parents will respond to questions about their child, not themselves and youth will answer about themselves. Phone calls will take about 30-60 minutes.

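### The readiness model for Hypothesis 1b has no period term, although T2C follows TAU in both clinics, so a shared time trend biases the T2C effect

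*Combined protocol and SAP*

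**What the plan says.** Study Objectives (Aim 1b) sets the scale: "To examine the feasibility of T2C in pediatric primary care clinics (n=2 clinics, 50 adolescents) using a stepped wedge design". Hypothesis 1b is directional: "Readiness for MH care will be greater among adolescents in T2C vs adolescents referred during TAU".

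Study Design & Methods gives the rollout: "All clinics will be initially monitored for at least 2 months during TAU, followed by a staggered adoption of T2C". Statistical Considerations repeats it and adds the step rule: "During each time period, a new clinic will begin to use T2C". Only the order of the clinics is randomised.

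The analysis appears twice in the same words, under Hypothesis 1b and in Statistical Considerations: "We will use generalized linear mixed models (nesting for site) to examine for between-intervention differences in readiness". Its covariate rule is: "Baseline characteristics that distinguish the groups will be included as covariates in models examining treatment effects".

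No section names period, step or calendar time as a model term. The week 4 and week 12 calls are timed from each participant's own baseline, so they do not stand in for calendar time.

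**The concern.** In a one-way rollout, treatment and calendar time move together. Nesting for site removes differences between clinics, but not a change over time that both clinics share. Randomising the order does not help, because T2C is later in both clinics under either order.

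The documents show two ways in which readiness could drift:

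- **At entry.** Youth can enter by several routes, the last of which is broad: "indicates depression OR provider indicates there is a concern that youth has mood or behavioral problem". If the mix of routes changes during the study, readiness may shift already at baseline.
- **At follow-up only.** Scientific Background names treatment availability as a barrier to care. If availability changes during the study, follow-up readiness could move while baseline readiness does not.

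In either case part of the trend would be reported as a T2C effect, with an interval that is valid only if there is no trend. The estimate could then mislead planning of a later trial.

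**Working it through.** **Inputs from the documents.** 2 clinics, 50 adolescents, both starting on TAU, one clinic switching per period. I read this as 3 periods: one TAU-only period plus one step per clinic. The plan states no alpha, power, SD, ICC or number of periods, so it has no figure to reproduce.

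**Assumptions not in the documents.** Total SD 1; one follow-up score per youth; ICC 0.05 to 0.10; baseline to follow-up correlation 0.6; covariate rule applied to baseline readiness at p<0.05; two-sided 5% test; common linear drift of d SD per period; no true effect.

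**Layout.**

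| | Period 0 | Period 1 | Period 2 |
|---|---|---|---|
| First clinic to switch | TAU, 8 | T2C, 8 | T2C, 9 |
| Second clinic to switch | TAU, 9 | TAU, 8 | T2C, 8 |

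This gives 25 youths per condition. Only period 1 has both conditions at once.

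**Bias, pooling clinics.** Mean period under T2C is (8×1 + 9×2 + 8×2)/25 = 1.68. Under TAU it is (8×1)/25 = 0.32. The difference is 1.36, so the bias is 1.36d. The correlation of T2C with period is 0.82.

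**Bias, within clinic (fixed site).**

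- Sum of squares of T2C: 25×(17/25)×(8/25) = 5.44 per clinic, 10.88 in total.
- Cross-product with period: 26 − 17×1.04 = 8.32 in the first clinic and 16 − 8×0.96 = 8.32 in the second, 16.64 in total.
- Bias: 16.64/10.88 = 1.53d. The within-clinic correlation is 0.87.

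Drifts of 0.1, 0.2 and 0.3 give biases of 0.15, 0.31 and 0.46 SD. A random site effect gives slightly less in this layout, 1.45d to 1.48d. Adding period indicators reduces the bias to zero.

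**Standard error, fixed site, ICC 0.05.** √(0.95/10.88) = 0.295 SD without period (average estimate 0.294). With period it is 0.59 SD (average estimate 0.588).

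**False-positive rates by simulation.** Ranges cover fixed and random site.

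| Model | d = 0.1 | d = 0.2 | d = 0.3 |
|---|---|---|---|
| Site, no baseline adjustment | 8–9% | 17–19% | 32–36% |
| Plan's rule, drift at baseline and follow-up | 6% | 11–12% | 19–20% |
| Plan's rule, drift at follow-up only | 7–8% | 17–19% | 32–36% |
| Always baseline readiness, no period, shared drift | 6% | 8% | 11–12% |
| Always baseline readiness, no period, follow-up-only drift | 10–11% | 24–26% | 46–49% |
| Site, period and baseline readiness | about 5% | about 5% | about 5% |

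Under shared drift the plan's rule leaves a bias of about 0.12, 0.23 and 0.31 to 0.32 SD. It protects weakly because, with 50 youths, baseline readiness is admitted in only about 9%, 17% and 31% of trials. With no drift the written model stays near nominal (4% to 6%).

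**Sensitivity, fixed site.**

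- Plan's rule, shared drift, correlation 0.3 to 0.8: 5–7%, 9–14% and 15–25%.
- Plan's rule, four unequal recruitment patterns: 6%, 10–11% and 17–19% for shared drift; 7%, 15–16% and 29–33% for follow-up-only drift.

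**The case against.** The best counter-argument is that readiness is measured at baseline as well as at follow-up, and the plan does not say how the mixed model uses the baseline score. If T2C were tested as change from baseline, drift shared by both time points would cancel: bias about 0, false positives about 5%, and root mean squared error (RMSE) 0.26 SD, against 0.48 SD for the proposed fix. That arithmetic is right. But the text compares readiness between conditions and treats baseline characteristics as covariates, so this is not the analysis described. Under follow-up-only drift a change analysis also keeps the full bias of 0.15, 0.31 and 0.46 SD.

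Other points stand in part:

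- **The covariate rule is wider than baseline readiness.** It covers demographic and clinical variables, and the plan gives no threshold. Another variable could pick up a changing entry mix. It would absorb drift only as far as it tracks it and happens to be admitted.
- **Total error is mostly larger with the fix.** RMSE is 0.48 SD, against 0.31, 0.36 and 0.43 for the written plan under shared drift, and 0.32, 0.42 and 0.54 under follow-up-only drift. This stands. The fix gives an unbiased estimate and an honest interval, not a smaller total error.
- **Clinic-by-period variation.** If it is 2% or 5% of the total variance, the fix itself gives about 8% or 12% false positives. At a shared drift of 0.1 that is no better than the written plan (7.7% or 11.6%). The fix does gain at drifts of 0.2 and above.
- **This is a feasibility trial with no stated alpha, and every drift size is assumed.** Both are true. They limit the weight of the percentages, but not the point that the model attributes a shared trend to T2C.

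**Conclusion.** The concern holds. That the period term is missing, and that T2C follows TAU in both clinics, comes directly from the text. A bias of about 1.5 times the drift per period follows from the 2-clinic, 3-period layout; other recruitment splits, with site random or fixed, give 1.17 to 1.53 times.

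The false-positive figures are less certain. They depend on the assumed drift, correlation, ICC and single follow-up score, and they should be read as a range. If there is no trend, the written model performs as intended. The plan gives no reason to assume that, and its covariate rule cannot correct drift that appears only at follow-up. This is a change worth making before analysis, not a flaw that invalidates the trial.

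**What to change.** In Study Objectives (Hypothesis 1b) and Statistical Considerations:

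1. Define the enrolment periods and add period as a fixed effect, with one indicator per step.
2. Always adjust for baseline readiness, whether or not the groups differ on it. The baseline call already collects it: "barriers to treatment, readiness for treatment, attitudes toward seeking psychological help". Baseline adjustment without period is not a substitute; it makes follow-up-only drift worse.
3. Enter clinic as a two-level indicator, since two clinics cannot support a variance estimate. With a random site effect, 39% to 51% of simulated fits put the site variance at zero. This is secondary, because the plan does not say that site is random.
4. Report the T2C−TAU difference with a t-based 95% confidence interval as a preliminary feasibility estimate, with no efficacy claim based on significance.
5. State two remaining limits: the interval leaves out clinic-by-period variation, and only two clinic orders can be randomised.
6. Keep the model without period as a sensitivity analysis, labelled as assuming no time trend.

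**Cost.** Wording only, no new data. The price is precision. With period alone the standard error doubles from 0.29 to 0.59 SD, and the interval half-width goes from 0.59 to 1.18 SD. With baseline readiness as well, the standard error is 0.48 SD and the half-width 0.96 SD at correlation 0.6; the standard error runs from 0.57 to 0.36 SD for correlations of 0.3 to 0.8. Without baseline adjustment, the drift at which the two models have equal RMSE is √(0.588² − 0.294²)/1.529 = 0.33 SD per period. The plan should disclose this cost.

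### The readiness model nests youths in site with only two clinics; read as a random clinic intercept, it adjusts for clinic unreliably, so clinic should be a fixed effect

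*Combined protocol and SAP*

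**What the plan says.** Study Objectives (Aim 1b) sets the size of the feasibility trial: "T2C in pediatric primary care clinics (n=2 clinics, 50 adolescents) using a stepped wedge design". Hypothesis 1b, in the same section, is the only hypothesis with a stated test: "Readiness for MH care will be greater among adolescents in T2C vs adolescents referred during TAU".

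The model is given in one sentence, identical in Study Objectives and in Statistical Considerations: "We will use generalized linear mixed models (nesting for site) to examine for between-intervention differences in readiness". The covariate rule follows it: "Baseline characteristics that distinguish the groups will be included as covariates in models examining treatment effects". Neither section says whether the site term is random or fixed. Neither names clinic or calendar period as a covariate, gives a small-cluster correction, or says what happens if the site variance is estimated as zero.

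On the rollout, Statistical Considerations says "All clinics will be initially monitored for at least 2 months during TAU, followed by a staggered adoption of T2C" and "During each time period, a new clinic will begin to use T2C", with the order randomised. With two clinics this gives three periods: TAU, T2C, T2C in the first clinic to cross, and TAU, TAU, T2C in the second.

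**The concern.** A random intercept borrows its degree of adjustment from the estimated between-clinic variance. With two clinics that estimate comes from a single contrast, the difference between two clinic means. When the contrast is no larger than sampling noise would produce, the estimate is zero and the fitted model is the one that would be obtained with clinic left out.

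This matters because a two-clinic stepped wedge does not balance treatment over clinics. The clinic that crosses first contributes more T2C youths and the other contributes more TAU youths. A stable difference in readiness between the clinics that is not fully adjusted for is therefore partly read as a T2C effect, in the trial's only hypothesis test. A fixed clinic indicator removes a stable difference completely, whatever its size.

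**Working it through.** **Inputs.** From the plan: 2 clinics, 50 adolescents, one-way staggered crossover. The plan gives no alpha, readiness SD, ICC, clinic difference, dropout or later period lengths, and no power figure to reproduce. Assumed: two-sided 5% test, continuous readiness with residual SD 1, one observation per youth, no dropout, 25 youths per clinic, near-equal steps (clinic A 8/8/9, clinic B 8/9/8, A crossing first), no true T2C effect.

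**Step 1: how often the clinic variance is zero.** For two clinics of 25, REML gives zero with probability P(F(1,48) < 1/(1 + 25·ICC/(1−ICC))).
- ICC 0: P(F < 1) = 0.678
- ICC 0.05: 25 × 0.05/0.95 = 1.316; P(F < 1/2.316) = 0.486
- ICC 0.10: 25 × 0.10/0.90 = 2.778; P(F < 1/3.778) = 0.391
- ICC 0.20: 25 × 0.20/0.80 = 6.25; P(F < 1/7.25) = 0.288

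Simulation with the treatment term in the model gave 68%, 50%, 40% and 29%. Under ML the shares were 86%, 69%, 58% and 44%.

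**Step 2: how much leaks if clinic drops out.** T2C youths: 17 from A and 8 from B. TAU youths: 8 from A and 17 from B. The leak is 17/25 − 8/25 = 0.36 of the clinic difference. If period terms are included and clinic drops out, only the middle period informs the T2C contrast (A on T2C, B on TAU), and the whole clinic difference passes through.

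**Step 3: size in the fitted model.** 8,000 simulated trials per setting, clinic A higher by 0.5 SD, t tests with residual degrees of freedom for both models:

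| Model | Mean T2C estimate, random clinic (REML) | Same, in trials with zero variance | Type I, random | Mean, fixed clinic | Type I, fixed |
|---|---|---|---|---|---|
| No period term (as written) | +0.052 SD | +0.186 SD (26.0% of trials) | 6.7% | −0.002 SD | 5.1% |
| With period terms | +0.168 SD | +0.489 SD (32.8% of trials) | 9.6% | −0.004 SD | 5.4% |

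A repeat without period terms gave +0.06 SD and 6.8% against 5.2%. ML with a Wald z test is worse (+0.090 SD and 8.5% without period terms, +0.297 SD and 15.0% with them), but part of that gap is the z reference.

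Without period terms the mean REML leak stays between +0.035 and +0.052 SD for clinic differences from 0.2 to 1.0 SD. At larger differences zero estimates become rare (57% at 0.2 SD, 1% at 1.0 SD).

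**Step 4: averaged over clinics and order.** With clinic effects drawn at random, the mean T2C estimate is about zero and the problem appears as excess rejection. For ICC 0.05 and 0.10, REML rejects 6.1% and 5.5% without period terms, and 7.3% and 7.8% with them. Fixed clinic rejects 4.7% to 5.1%.

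**Step 5: precision.** Without period terms, the SE ignoring clinic is √(1/25 + 1/25) = 0.283. With clinic fixed it is 0.283/√(1 − 0.36²) = 0.303. With period terms and clinic fixed, the middle-period contrast has variance 1/8 + 1/9 = 0.236. The clinic difference estimated from the other two periods has variance 1/(1/0.250 + 1/0.236) = 0.121. The SE is √0.357 = 0.598.

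**Step 6: what a fixed clinic effect leaves.** With clinic fixed, no period term and an assumed trend of 0.25 SD per period, T2C youths are observed about 1.5 periods later than TAU youths in the same clinic. The spurious effect is about 1.5 × 0.25 = 0.38 SD; the simulated type I error is 22.5%.

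**The case against.** The strongest reply is that little is lost under the plan as written. Without period terms the two models are about equally accurate: root-mean-square error, random against fixed clinic, is 0.289 against 0.302 with no clinic difference and 0.310 against 0.304 at 0.5 SD. A leak of 0.05 SD beside a standard error of 0.30 SD would not change what a 50-youth feasibility study can conclude. This stands, and it sets the weight of the point.

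Four stronger readings are tempting, and the documents do not support them.
- A reader might infer that the plan states a random clinic effect. It does not. Readiness is collected at baseline and at weeks 4 and 12, so the mixed structure could also serve repeated visits. A random site intercept is the likelier meaning of nesting for site, but it is an inference.
- A reader might take the 0.17 SD bias and 9% to 10% type I error as properties of the planned analysis. Those need period terms, and the plan names none.
- A reader might infer a systematic bias in favour of T2C. The sign depends on whether the first clinic to cross is the higher-scoring one, and the order is randomised. What remains is that the trial will have one realised order, and its estimate will carry that imbalance.
- A reader might treat the 68% zero-variance figure as a measure of harm. Zeros are commonest when there is no clinic difference to leak.

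**Conclusion.** The point holds at moderate weight: the change should be made, but the analysis as written is not badly broken. Two clinics cannot support a useful between-clinic variance, and the plan has no provision for the zero estimate that will often result. The harm under the written model is small, a type I excess of about 1.5 percentage points (6.7% against 5.2%) at an assumed 0.5 SD clinic difference. It becomes material if calendar period is added, as a stepped wedge normally needs.

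The zero-variance shares depend on the assumed 25 per clinic and on ICC. The leak depends on the near-equal steps, the assumed clinic difference and a continuous outcome. The documents fix none of these.

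A fixed clinic effect is an improvement but does not by itself make the interval valid. An unmodelled time trend can do more damage than the clinic leak. With an assumed clinic-by-period variance of 0.02, fixed clinic without period terms still rejects 6.6%, and two clinics cannot estimate that variance well.

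**What to change.** In Study Objectives (Hypothesis 1b) and Statistical Considerations, replace the site-nested mixed model with a generalized linear model for readiness that has clinic as a fixed effect (one indicator) and t-based intervals on residual degrees of freedom. Keep a youth-level random effect only if repeated visits are modelled together. State that inference applies to these two clinics. In the same edit, say how calendar period is handled.

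The cost is a sentence or two in each place and one degree of freedom for clinic. Without period terms the SE is 0.303 SD, against 0.283 if clinic were ignored; the difference detectable with 80% power goes from 0.79 to 0.85 SD. With period terms the price is real: when the clinics do not differ, the simulated SD of the estimate is 0.597 against 0.526 for the random intercept, about 29% more variance (0.597²/0.526² = 1.29). The detectable difference is then 1.68 SD (2.80 × 0.598). That is what two clinics can support with both terms in the model, and the plan should report it as such.

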#### Consent:

Within about 24-48 hours, the ETUDES Assessment & Recruitment Center (ARC) assessors will call an eligible teen to complete informed consent with teen and parent, conduct baseline assessment measures, and onboard the T2C program on the cell phone. A waiver to document consent will be used to obtain consent from parents and assent from minors (12-17 yo) over the phone with the ARC assessor. If a minor participant turns 18 yo during the course of the study, a waiver to document consent will be used to identify if the minor wishes to continue their participation in the study. Date and time of the informed consent & assent phone conversation will be recorded. Prior to this phone call the RA in the primary care practice will have provided the family with a copy of the informed consent wording and HIPAA authorization to review (See recruitment methods section). The ARC assessor will review any areas of concern or question before obtaining family consent and moving on with the Baseline data collection. Consenting will take about 15 minutes.

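### The readiness analysis does not name baseline readiness as a covariate; under the stated rule it would enter only if the groups happened to differ on it

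*Combined protocol and SAP*

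**What the plan says.** Study Objectives (Aim 1b) states the hypothesis: "Readiness for MH care will be greater among adolescents in T2C vs adolescents referred during TAU". The Baseline assessment phone call section lists readiness among the measures ("barriers to treatment, readiness for treatment, attitudes toward seeking psychological help"). The Consent section puts that call ahead of the start of the intervention: assessors "conduct baseline assessment measures, and onboard the T2C program on the cell phone". The Follow Up assessment phone calls section collects readiness again at weeks 4 and 12.

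The analysis is described in nearly the same words in Study Objectives and in Statistical Considerations. Group comparisons come first ("We will first conduct t tests for continuous variables and chi square tests for categorical variables"), and their purpose is "to examine for baseline differences in demographic and clinical variables". Then: "We will use generalized linear mixed models (nesting for site) to examine for between-intervention differences in readiness". The covariate rule follows: "Baseline characteristics that distinguish the groups will be included as covariates in models examining treatment effects". No cut-off is given for what counts as distinguishing the groups. Readiness is not named among the variables to be compared. It is not named in the model either, whether as a covariate or as a repeated time point.

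**The concern.** The baseline value of an outcome is often its strongest single predictor. Here it is on the measurement schedule, but it has no assured place in the model. It would enter only if two things hold: readiness counts as a clinical variable, and the two groups differ on it. Because the rule follows directly on t and chi-square tests, it appears to mean a test result; that is an inference.

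Precision is at stake first. If the groups are comparable, leaving baseline readiness out causes no bias but widens the interval. Bias comes second. T2C and TAU youths enrol at different times ("During each time period, a new clinic will begin to use T2C"), so a difference in baseline readiness is possible, and a test with 50 youths will often miss it. The documents show no such difference. Third, the covariate set is not known until the data are seen.

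**Working it through.** **Inputs from the documents.** 50 adolescents in 2 clinics (Study Objectives, Aim 1b); readiness at baseline, week 4 and week 12; a mixed model with site; a covariate rule with no cut-off. No alpha, power, effect size, SD, correlation or group split is stated, so there is no planned figure to reproduce.

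**Assumed.** 25 youths per condition over 2 clinics and 3 periods (one clinic 8 TAU and 17 T2C, the other 17 and 8); two-sided 0.05; normal outcome with SD 1; one follow-up; no dropout; site as a fixed effect; effect 0.6 SD; rule cut-off 0.05; the same baseline call for TAU youths; r from 0 to 0.7. Simulated values use 100,000 trials per setting.

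**1. How often readiness enters.** With comparable groups, a 0.05 test selects it in 5% of trials and omits it in 95%.

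**2. Precision by formula.** SE without baseline readiness = 1/√(2 × 8 × 17/25) = 1/√10.88 = 0.303. Always adjusting multiplies the variance by about (1 − r²)(1 + 1/45):
- r = 0.3: 0.91 × 1.022 = 0.930; SE 0.303 × √0.930 = 0.292
- r = 0.5: 0.75 × 1.022 = 0.767; SE 0.265
- r = 0.7: 0.51 × 1.022 = 0.521; SE 0.219

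Break-even is where the factor equals 1: r² = 1/46, so r is about 0.15.

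**3. Simulation, no imbalance.**

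| | r = 0.3 | r = 0.5 | r = 0.7 |
|---|---|---|---|
| SD of estimate, stated rule | 0.301 | 0.295 | 0.284 |
| SD of estimate, always adjusted | 0.293 | 0.266 | 0.219 |
| Squared ratio | 1.06 | 1.23 | 1.68 |
| Power, rule | 49.3% | 49.3% | 50.3% |
| Power, always | 52.0% | 60.0% | 76.6% |
| Gain (points) | 2.7 | 10.7 | 26.3 |
| Power with period term, rule | 16.8% | 16.5% | 16.7% |
| Power with period term, always | 17.7% | 20.0% | 27.5% |
| Gain (points) | 0.9 | 3.5 | 10.8 |

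The squared ratio is the relative number of youths the rule needs to match always adjusting: about 6%, 23% and 68% more (within about 0.02 on the ratio between runs). At a looser 0.20 cut-off the excess is 3%, 12% and 38%. A separate run put the gain at r = 0.5 at 10 points. At r = 0, always adjusting loses about half a point to one point of power.

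**4. If the groups truly differ by 0.5 SD at baseline** (r = 0.3, 0.5, 0.7).
- Difference acting through the measured score: the rule omits readiness in 59% of trials and leaves a mean bias of 0.058, 0.093 and 0.132 SD. Always adjusting leaves 0.001 or less. The rule's type I error is 0.053, 0.059 and 0.063.
- Stable difference measured with error: always adjusting leaves (1 − r) × 0.5 = 0.35, 0.25 and 0.15 SD, against 0.41, 0.34 and 0.28 under the rule. Type I error is 0.21, 0.15 and 0.10, against 0.26, 0.20 and 0.15.

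**5. Keeping the plan's rule for other covariates.** Take a second covariate, independent of readiness, that differs by 0.5 SD and has outcome coefficient 0.3. Unadjusted, it contributes 0.5 × 0.3 = 0.15 SD of bias.
- Stated rule alone: bias about 0.05 SD, type I error about 0.05.
- Readiness always in, other adjustment removed: bias about 0.15 SD, type I error 0.08 to 0.11.
- Readiness always in, rule kept for the rest: bias about 0.05 SD, and the lowest root mean squared error of the three for r = 0.3 to 0.7.

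**The case against.** The strongest reply is that the plan is brief and the concern rests on its silence. A mixed model with three readiness measurements could already carry baseline as a repeated outcome, and the rule could admit readiness as a clinical variable. Both are possible, but neither is written, and one sentence would settle it. The reply also notes that the readiness scale and link are not stated, so figures in SD units may not transfer. It adds that a baseline call for TAU youths is inferred, since the call sections are written around T2C onboarding. Both stand as caveats. The planned baseline comparison does imply baseline data in both groups.

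Three stronger readings are tempting, and the documents do not support them.
- A reader might infer that adjustment driven by observed differences should be moved out of the primary model. Youths are not individually randomised and the groups enrol at different times, so differences can be systematic. Step 5 shows that removing this protection roughly triples the bias from another imbalanced covariate.
- A reader might infer that a change-score contrast should be ruled out, or baseline means constrained to be equal. Without imbalance, the change score is less precise than always adjusting at each r examined (SD 0.359, 0.304 and 0.235 at r = 0.3, 0.5 and 0.7). But it is the unbiased choice in the stable-difference case of step 4, and the documents do not say which mechanism holds. An equal-baseline constraint normally rests on randomising individuals, which is absent here.
- A reader might infer that the rule biases the trial or breaks its type I error. The documents show no imbalance, and without one the rule is unbiased and type I error is not inflated (0.038 to 0.049).

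**Conclusion.** The point holds as a gap in pre-specification with a precision cost. Baseline readiness is on the schedule, is not named in the model, and under the only stated rule would usually be left out when the groups are comparable. The size of the loss is conditional: nil near r = 0.15, small at r = 0.3, substantial at r = 0.5 and above. A period term cuts the gain to less than half, and power for 0.6 SD then stays at 28% or below either way. All of this rests on the assumed split, effect, cut-off and correlations.

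If the groups truly differ in stable readiness that is measured with error, always adjusting reduces the bias but does not remove it. Calendar-time confounding is a separate question that this change does not address. Severity is minor to moderate: Aim 1b is a feasibility trial with no power target, though it does state a directional hypothesis and a model for it.

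**What to change.** In Study Objectives (Hypothesis 1b) and Statistical Considerations, state that baseline readiness is always a covariate in the week 4 and week 12 readiness models, whatever the baseline comparison shows. Keep site in the model. Keep the existing adjustment for other baseline characteristics that distinguish the groups, and state the cut-off that defines it. Confirm that TAU youths have the same baseline readiness assessment. If baseline was meant to enter as a repeated measure instead, say so and say how the treatment contrast is formed.

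The cost is a few sentences of wording and one degree of freedom, which is about one power point or less if baseline readiness turns out to be unrelated to the outcome. If TAU youths have the same call, no new visits, data or participants are needed.
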